6.1.2 Response Assessment

Patients who do not meet the cCR definition (section 6.1.1) during the evaluation at 12-14 weeks post-treatment will undergo pathologic evaluation as outlined in section 5.3.

6.1.3 Outcomes Assessment

Patients will be assessed for oncologic outcomes including LRC, PFS, and OS at 12-14 weeks post-treatment and at subsequent follow-ups at 6 and 12 months.

6.2 Safety/Tolerability

Analyses will be performed for all subjects having received at least one fraction of radiation. The study will use the CTCAE version 5.0 for reporting of adverse events. https://ctep.cancer.gov/protocolDevelopment/electronic_applications/ctc.htm

6.3 Quality of life

6.3.1 UW-QOL

UW-QOL (Appendix C) is a concise patient-reported QOL survey with 12 domains including pain, appearance, activity level, recreation, swallowing, chewing, speech, shoulder function, taste, saliva, depression, and anxiety (25). A composite score can be derived for physical and social/emotional subscales. The most recent version, version 4, has incorporated mood and anxiety to capture the emotional QOL of patients with head and neck cancer (25).

6.3.2 MDADI

MDADI (Appendix D) is a validated self-assessment to specifically assess dysphagia's impact on the quality of life of patients with head and neck cancer (26). It is scored on a scale of 20 to 100 with higher score denoting better quality of life. MDADI is divided into subscales including functional, physical, emotional, and global domains with a combined composite score. A 10-point difference in score has been shown to be clinically meaningful (27).

6.3.3 EQ-5D-5L

EQ-5D-5L (Appendix E) is one of the most widely used assessment of health status and QOL internationally, composed of 5 items to address mobility, self-care, usual activities, pain/discomfort, and anxiety/depression with an update in 2011 to expand each response to five levels (from three levels previously) (28).

7.0 ADVERSE EVENTS

7.1 Experimental Therapy

Experimental therapy is de-intensified hypofractionated radiation therapy. Concurrent chemotherapy is considered standard of care.

7.1.1 Contraindications

There are no special contraindications for this study beyond typical contraindications to radiation therapy or chemotherapy.

7.1.2 Special Warnings and Precautions for Use

None

7.1.3 Interaction with other medications

None

7.1.4 Adverse Reactions

Head and neck radiotherapy and chemoradiotherapy are associated with potential acute and late toxicities.

- Acute adverse reactions:
 - Fatigue and weight loss
 - Loss of taste and appetite
 - Dysphagia and odynophagia
 - Mucositis
 - Dermatitis
- Late adverse reactions:
 - Dysphagia
 - Xerostomia
 - Altered taste
 - Lymphedema
 - Soft tissue damage (rare)
 - Osteoradionecrosis (rare)
 - Nerve or neurologic damage (rare)

7.2 Adverse Event Monitoring

Adverse event data collection and reporting, which are required as part of every clinical trial, are done to ensure the safety of subjects enrolled in the studies as well as those who will enroll in future studies. Adverse events are assessed in a routine manner at scheduled times during a trial. Additionally, certain adverse events must be reported in an expedited manner to allow for optimal monitoring of subject safety and care.

All subjects experiencing an adverse event, regardless of its relationship to study therapy, will be monitored until:

- the adverse event resolves or the symptoms or signs that constitute the adverse event return to baseline or is stable in the opinion of the investigator;
- there is a satisfactory explanation other than the study therapy for the changes observed; or
- death.

7.2.1 Definitions

An adverse event is defined as any untoward or unfavorable medical occurrence in a human research study participant, including any abnormal sign (for example, abnormal physical exam, imaging finding or clinically significant laboratory finding), symptom, clinical event, or disease, temporally associated with the subject's participation in the research, whether or not it is considered related to the subject's participation in the research.

Adverse events encompass clinical, physical and psychological harms. Adverse events occur most commonly in the context of biomedical research, although on occasion, they can occur in the context of social and behavioral research. Adverse events may be expected or unexpected.

Acute Adverse Events

Adverse events occurring in the time period from the signing of the informed consent, through 90 days post treatment will be considered acute adverse events. The protocol will separately define Dose Limiting Toxicity in section 9.1 as applicable.

Late Adverse Events

Adverse effects occurring in the time period from the end of acute monitoring, to 12 months post treatment, will be defined as late adverse events. The study team will review encounters in the following select specialty categories relevant to study endpoints: radiation oncology, medical oncology, and otolaryngology. The queried

encounters will be limited in scope based on categorization of events; namely, encounters that are related to any head and neck or gastrointestinal event or problem.

Severity

Adverse events will be graded by a numerical score according to the defined NCI Common Terminology Criteria for Adverse Events (NCI CTCAE) Version 5.0. Adverse events not specifically defined in the NCI CTCAE will be scored on the Adverse Event log according to the general guidelines provided by the NCI CTCAE and as outlined below.

- Grade 1: Mild
- Grade 2: Moderate
- Grade 3: Severe or medically significant but not immediately life threatening
- Grade 4: Life threatening consequences
- Grade 5: Death related to the adverse event

Serious Adverse Events

OHRP and UTSW HRPP define serious adverse events as those events, occurring at any dose, which meets any of the following criteria:

- results in death;
- is life-threatening (places the subject at immediate risk of death from the event as it occurred);
- results in inpatient hospitalization^{1,2} or prolongation of existing hospitalization;
- results in a persistent or significant disability/incapacity;
- results in a congenital anomaly/birth defect; or
- based upon appropriate medical judgment, may jeopardize the subject's health and may require medical or surgical intervention to prevent one of the other outcomes listed in this definition.

Note: A "Serious adverse event" is by definition an event that meets **any** of the above criteria. Serious adverse events may or may not be related to the research project. A serious adverse event determination does not require the event to be related to the research. That is, both events completely unrelated to the condition under study and events that are expected in the context of the condition under study may be serious adverse events, independent of relatedness to the study itself. As examples, a car accident requiring ≥24 hour inpatient admission to the hospital would be a serious adverse event for any research participant; likewise, in a study investigating end-stage cancer care, any hospitalization or death which occurs during the protocol-specified period of monitoring for adverse and serious adverse events would be a serious adverse event, even if the event observed is a primary clinical endpoint of the study.

¹Pre-planned hospitalizations or elective surgeries are not considered SAEs.

Note: If events occur during a pre-planned hospitalization or surgery, that prolong the existing hospitalization, those events should be evaluated and potentially reported as SAEs.

²NCI defines hospitalization for expedited AE reporting purposes as an inpatient hospital stay equal to or greater than 24 hours. Hospitalization is used as an indicator of the seriousness of the adverse event and should only be used for situations where the AE truly fits this definition and NOT for hospitalizations

associated with less serious events. For example: a hospital visit where a patient is admitted for observation or minor treatment (e.g. hydration) and released in less than 24 hours. Furthermore, hospitalization for pharmacokinetic sampling is not an AE and therefore is not to be reported either as a routine AE or in an expedited report.

7.2.2 Unanticipated Problems Involving Risks to Subjects or Others (UPIRSOs):

The phrase “unanticipated problems involving risks to subjects or others” is found, but not defined in the HHS regulations at 45 CFR 46, and the FDA regulations at 21 CFR 56.108(b)(1) and 21 CFR 312.66. Guidance from the regulatory agencies considers unanticipated problems to include any incident, experience, or outcome that meets ALL three (3) of the following criteria:

- Unexpected in terms of nature, severity or frequency given (a) the research procedures that are described in the protocol-related documents, such as the IRB-approved research protocol and informed consent document; and (b) the characteristics of the subject population being studied;
AND
- Related or possibly related to participation in the research (possibly related means there is a reasonable possibility that the incident, experience, or outcome may have been caused by the procedures involved in the research);
AND
- Suggests that the research places subjects or others at greater risk of harm (including physical, psychological, economic, or social harm) than was previously known or recognized. Note: According to OHRP, if the adverse event is serious, it would always suggest a greater risk of harm.

Follow-up

All adverse events will be followed up according to good medical practices.

7.3 Steps to Characterize a Serious Adverse Event for Reporting to the SCCC DSMC

Step 1: Identify the type of adverse event using the NCI Common Terminology Criteria for Adverse Events (CTCAE v5).

Step 2: Grade the adverse event using the NCI CTCAE v5.

Step 3: Determine whether the adverse event is related to the protocol therapy.

Attribution categories are as follows:

- Definite – The AE is *clearly related* to the study treatment.
- Probable – The AE is *likely related* to the study treatment.
- Possible – The AE *may be related* to the study treatment.
- Unlikely – The AE *may NOT be related* to the study treatment.
- Unrelated – The AE is *clearly NOT related* to the study treatment.

Note: This includes all events that occur within 30 days of the last dose of protocol treatment. Any event that occurs more than 30 days after the last dose of treatment and is attributed (possibly, probably, or definitely) to treatment must also be reported as indicated in the sections below.

Step 4: Determine the expectedness of the adverse event. Expected events are those that have been previously identified as resulting from administration of the treatment. An adverse event is considered unexpected, for expedited reporting purposes only, when either the type of event or the severity of the event is not listed in:

- the current known adverse events listed in the Agent Information Section of this protocol (if applicable);
- the drug package insert (if applicable);
- the current Investigator's Brochure (if applicable)
- the Study Agent(s)/Therapy(ies) Background and Associated Known Toxicities section of this protocol

7.3.1 Reporting SAEs and UPIRSOs to the Simmons Comprehensive Cancer Center (SCCC) Data Safety Monitoring Committee (DSMC)

SAEs and UPIRSOs at all sites, which occur in research subjects on protocols for which the SCCC is the DSMC of record require reporting to the DSMC regardless of whether IRB reporting is required. **All SAEs occurring during the protocol-specified monitoring period and all UPIRSOs should be submitted to the SCCC DSMC within 5 business days of the study team members awareness of the event(s).** In addition, for participating centers other than UTSW, local IRB guidance should be followed for local reporting of serious adverse events or unanticipated problems.

The UTSW study PI is responsible for ensuring SAEs/UPIRSOs are submitted to the SCCC DSMC Coordinator. This may be facilitated by the IIT project manager, study team, sub-site or other designee. Electronic versions of the eIRB Reportable Event report; FDA Form #3500A forms, or other sponsor forms, if applicable; and/or any other supporting documentation available should be submitted to the DSMC.

UT Southwestern and affiliated will submit documentation via the SAE submission portal. All subsites participating in multi-center study may utilize the Serious Adverse Event Template and submit to the IIT Project Manager, or designee. The DSMC Coordinator will route the form to the DSMC Chair who determines if immediate action is required. Follow-up eIRB reports, and all subsequent SAE or UPIRSO documentation that is available are also submitted to the DSMC Chair who determines if further action is required via the same process. *(See Appendix V of the SCCC DSMC Plan for instructions on how to submit SAEs through the portal and for a template Serious Adverse Event Form which may be utilized by subsites on multi-center IIT studies).*

Events that do NOT meet UPIRSO criteria should be tracked, evaluated, summarized, and submitted to the UTSW HRPP/IRB at continuing review.

For more information on UTSW HRPP/IRB reportable event policy, see https://www.utsouthwestern.edu/research/hrpp/assets/policy_9.5reportable.pdf

7.4 Unblinding Procedures

Not applicable to current protocol.

7.5 Stopping Rules

The primary hypothesis of the phase 1 study is that de-intensified HFRT is safe and tolerable. The trial will terminate during the rolling 6 dose escalation phase if it has reached level -1 and 2 patients experience dose limiting toxicity (DLT) at this dose level.

The secondary hypothesis is that the crude 1-year LRC rate is at least 85% (based on historical controls). In other words, for the target of 20 evaluable patients at 1 year, up to 3

patients can have a LRR and satisfy the pre-specified hypothesis. Thus, if a 4th patient enrolled on the trial experiences LRR within 1 year of completing the study treatment, the trial will be terminated for futility.

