4.1.2 Dose and fractionation

Dose calculation for HFRT was based on the biologically effective dose (BED) model accounting for time/repopulation observed in HNSCC:

$$BED = n(d/[\alpha/\beta]) - \log_2(T - Tk)/\alpha T p$$

n = number of fractions

d = dose per fraction

T = overall treatment time

Conventionally fractionated RT: 40 days (30 fractions)

Hypofractionated RT: 19 days (12-15 fractions), 26 days (20 fractions)

Tk = time delay of repopulation (21 days for tumor, 7 days for mucosa)

Tp = cell doubling time (3 days for tumor, 2.5 days for mucosa)

$\alpha/\beta = 3$ for late complications, 10 for tumor/mucosa

$\alpha = 0.35 \text{ Gy}^{-1}$

Dose and fractionation were selected to satisfy two parameters (see Table):

- $\leq \text{BED}_3$ vs conventional fractionation (60 Gy), i.e. late toxicity dose to normal tissue
- $\geq \text{BED}_{10}$ vs conventional fractionation (60 Gy), i.e. dose to tumor

Table. Total dose BED calculation for HFRT (vs comparison [conventional fractionation])

Level	Dose	BED /w repopulation $\alpha/\beta = 10$ (tumor)	BED /w repopulation $\alpha/\beta = 10$ (acute mucosa)	BED $\alpha/\beta = 3$ (late normal tissue)
1*	44.4 Gy/12 fx (3.7 Gy/fx), 4 fx/week	64	52	99
0	46.5 Gy/15 fx (3.1 Gy/fx), 5 fx/week	61	51	95
-1	52 Gy/20 fx (2.6 Gy/fx), 5 fx/week	62	50	97
Comparison	60 Gy/30 fx (2 Gy/fx), 5 fx/week	59	46	100

Abbreviations: fx, fraction(s)

*Level 1 eliminated at time of amendment. See the end of the section for details.

Level 0 will test a 15-fraction HFRT regimen treated 5 times a week for 3 weeks. If successful, level 1 will test a 12-fraction HFRT regimen treated 4 times a week for 3 weeks. If level 1 is well-tolerated, this regimen will be considered maximally tolerated dose/fractionation (i.e. no further reduction in the number of fractions).

If Level 0 is deemed intolerable, patients will be enrolled on level -1, which will test a 20-fraction HFRT regimen treated 5 times a week for 4 weeks. Given published literature on 20-fraction regimens, we anticipate that a 20-fraction regimen will be tolerable.

The calculated BED for acute toxicity such as the normal mucosa may be slightly increased vs conventionally fractionated RT, but the dose ranges **are well below** the limits deemed tolerable (<59-63 Gy₁₀) based on analysis of toxicities associated with various head and neck cancer fractionation regimens published to date (23).

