8.1.1 Return and Retention of Study Drug Not applicable

9.0 STATISTICAL CONSIDERATIONS

9.1 Study Design/Study Endpoints

9.1.1 Study design:

Phase I Rolling 6 design with dose expansion cohort
 Study design will be a rolling 6 dose escalation study, a modification to the standard 3 + 3 design (29). In contrast to the 3 + 3 design where patients are enrolled in cohorts of 3, the rolling 6 design allows for continuous enrollment up to a total of 6 patients at the same dose level. The dose level assigned to a new patient is based on the number of patients currently enrolled and evaluable, and the number of patients experiencing a DLT. Once six patients have been enrolled at the current dose level, enrollment will stop until at least 5 of the 6 patients have completed evaluation for DLT. Escalation to the next dose level occurs if at time of enrollment 3/3, 4/4, 5/5, 5/6, or 6/6 patients at the dose level are evaluated for and without DLT. De-escalation occurs if at the time of enrollment, 2 or more patients have experienced a DLT at the dose level.

DLT definition:

- Any CTCAE grade 4 toxicity (generally described as life-threatening consequences with urgent intervention indicated) attributed to RT during and up to 3 months post-treatment
- Persistent CTCAE grade 3 mucositis at 3 months post-treatment
 - CTCAE definitions:
 - Oral mucositis: severe pain; interfering with oral intake
 - Pharyngeal mucositis: severe pain; unable to adequately aliment or hydrate orally; limiting self-care ADL
 - To decrease subjectivity of interpretation by each clinician, the definition for grade 3 mucositis was consolidated as below:
 - Severe pain defined as needing daily opioid use of >30 morphine equivalent dose during the past week for mucositis, AND
 - The pain interferes with oral intake or swallowing defined as tolerating a liquid only diet or requiring tube feeds (with the exception of patients who were on a liquid only diet at baseline prior to RT, in which case they would need to be feeding tube dependent to satisfy this definition).

MTD definition: highest dose/fractionation level among those listed in section 4.1.2 at which ≤ 1 of 6 patients have experienced a DLT.

During the dose expansion phase, patients will be enrolled at MTD to reach the total accrual goal of 24 patients.

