9.3 Data Analyses

9.3.1 Primary endpoint

9.3.1.1 MTD

Acute toxicity will be assessed weekly during treatment and 2 weeks, 1, 2, and 3 months post-treatment to assess for DLT to determine the MTD as outlined in Section 9.1.1.

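### The primary hypothesis of safety and tolerability rests only on a six-patient level-selection rule; report the DLT rate with an exact bound over all evaluable patients at the selected level

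*Combined protocol and SAP*

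**What the plan says.** Section 7.5 (Stopping Rules) states: "The primary hypothesis of the phase 1 study is that de-intensified HFRT is safe and tolerable". No DLT rate is attached. The rule that follows ends the trial during escalation "if it has reached level -1 and 2 patients experience dose limiting toxicity (DLT) at this dose level".

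Two provisions lead to level -1. Section 9.1.1 says "De-escalation occurs if at the time of enrollment, 2 or more patients have experienced a DLT at the dose level", and section 4.1.2 says "If Level 0 is deemed intolerable, patients will be enrolled on level -1". Level 1 was removed by amendment, so levels 0 and -1 are the only ones left.

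Section 9.1.1 defines the MTD as the "highest dose/fractionation level among those listed in section 4.1.2 at which ≤ 1 of 6 patients have experienced a DLT". The primary analysis in 9.3.1.1 collects acute toxicity "to assess for DLT to determine the MTD as outlined in Section 9.1.1" and adds no estimate, interval or limit.

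The time and events table (5.4) restricts DLT assessment to the escalation phase. Section 5.2 places weekly visits in the expansion phase outside trial procedures. Section 9.2 sets a total of 24 patients.

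By contrast, the secondary hypothesis in 7.5 has a rate (1-year locoregional control of at least 85%), a denominator (20 evaluable) and a failure count (the fourth recurrence).

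**The concern.** A stated hypothesis of safety needs some quantity by which it can be judged. Here the only DLT criterion is the at-most-1-of-6 rule, which exists to choose a level. It is compatible with high true DLT rates, and two levels can be tried in turn.

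The expansion patients add nothing to the primary conclusion. If level 0 is selected after six patients, 24 - 6 = 18 more are treated there; DLTs in any of them would leave the primary conclusion unchanged as written. A reader who takes the named MTD as evidence of tolerability would be relying on about six patients, although up to 24 may have been treated at that level.

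**Working it through.** **Inputs from the plan.** MTD criterion of at most 1 DLT in 6, and de-escalation at 2 or more (9.1.1). Two remaining levels (4.1.2). Total of 24, target of 20 evaluable at 1 year, 15% attrition (9.2).

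**Assumptions that are not in the plan.** Patients are independent. A true DLT rate of 1/3 is used for illustration, because the documents give no unacceptable rate; 25% and 40% are shown as a range. Where two levels are combined, the rate is taken as equal at both.

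**The plan's own figure.** 20 / (1 - 0.15) = 23.5, rounded up to 24, which reproduces. The plan states no operating characteristic for the DLT rule, so there is none to reproduce.

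**What the selection rule shows.** The one-sided 95% Clopper-Pearson upper bound is the value of p at which P(X ≤ x | n, p) = 0.05.
- 0/6: 1 - 0.05^(1/6) = 39.3%
- 1/6: (1-p)^6 + 6p(1-p)^5 = 0.05 gives p = 58.2%

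**Chance that one level passes, six evaluated.** P(X ≤ 1) = (1-p)^6 + 6p(1-p)^5. At p = 1/3 this is 0.0878 + 0.2634 = 0.351, so the level fails with probability 0.649.

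**Chance that some level is named, same rate at both.** 1 - (fail)^2 = 1 - 0.649^2 = 0.579.

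| Assumed true DLT rate | One level passes | Some level named (equal rates) |
|---|---|---|
| 25% | 53% | 78% |
| 1/3 | 35% | 58% |
| 40% | 23% | 41% |

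**Effect of a conflict in the text.** The paragraph on eliminating level 1, at the end of 4.1.2, makes expansion conditional on level 0 showing no DLTs. Read literally, that is stricter than 9.1.1. If any DLT at level 0 sent the trial to level -1, the figure at 1/3 would be 1 - (1 - 0.0878) × 0.649 = 0.41 with six evaluated per level.

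**What the expansion patients would add.** One-sided 95% exact upper bounds at the selected level:
- 3/24: 29.2%
- 3/20: 34.4%
- 2/18: 31.0% (18 is the number at level -1 if six patients were first treated at level 0)

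**The case against.** **No passage says that naming an MTD confirms the hypothesis.** The sentence in 7.5 introduces a stopping rule, while the primary objective, endpoint and analysis are all determination of the MTD. This stands. A reader might infer that any named MTD will be reported as proof of safety, but that is a prediction about the report and not something the plan states. What remains is that a primary hypothesis is stated with no other criterion for judging it.

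**Tolerability is judged level by level.** A failure at level 0 followed by a pass at level -1 means that level 0 was not tolerated and level -1 was selected. It is not a blanket finding of safety. This also stands, so the single-level 35% is the cleaner figure. The 58% needs equal rates at both levels. The 4.1.2 table gives modelled acute mucosal BED of 51 and 50, which makes equality a fair scenario. However, the plan expects the 20-fraction level to be tolerable, and if it truly is less toxic, a pass there is correct.

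**A figure of 67% is tempting.** It follows if a level also clears on 3/3, from the 9.1.1 rule "Escalation to the next dose level occurs if at time of enrollment 3/3, 4/4, 5/5, 5/6, or 6/6 patients at the dose level" without DLT. That is the escalation rule. Escalation was eliminated, and the MTD is the level "at which ≤ 1 of 6 patients have experienced a DLT". At the planned 3 patients a month, six enrol in about two months, before the first has completed roughly three weeks of treatment and three months of DLT follow-up. The 3/3 route should not carry the argument.

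**Other safety evidence exists.** Rates of grade 3 or higher toxicity and feeding-tube dependence are secondary endpoints, safety analyses cover everyone given one fraction (6.2), and the DSMC reviews adverse events quarterly (10.4). This is true, although none of it has a stated limit or interval or is tied to the primary hypothesis.

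**A confirmatory test does not suit a phase I trial of this size.** That is a reasonable position, and no such test is required here.

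**Conclusion.** The point holds as one about the conclusion and its reporting. It does not show a fault in the rolling-6 rule. Section 7.5 states a safety hypothesis that the primary analysis can address only through at most 1 of 6, and that result leaves upper bounds of 58% (1/6) or 39% (0/6) on the DLT rate. These bounds need only independent patients with a common DLT rate within the level.

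The pass probabilities rest on more: 35% for one level assumes a true rate of 1/3, and 58% for some level also assumes that rate at level -1. Neither assumption comes from the plan. The 2-of-6 de-escalation trigger is an observed count and not a declared limit on the true rate. The documents therefore do not support saying that the plan would declare an unacceptable regimen safe most of the time. They do support saying that a named MTD carries little evidence of tolerability by itself, and that the expansion patients, who could supply more, are left out of the DLT assessment. Correcting this is an inexpensive improvement; dose assignment is unaffected.

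**What to change.** Leave the selection, de-escalation and stopping rules unchanged.

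1. In 7.5 and 9.3.1.1, state that at most 1 of 6 only selects the level for expansion.
2. Replace the claim of safety and tolerability in 7.5 with an estimate: the DLT proportion among all DLT-evaluable patients treated at the selected level, escalation plus expansion, with a one-sided 95% Clopper-Pearson upper bound. Specify this in 9.3.1.1 and define DLT-evaluable.
3. Amend 5.2 and 5.4 so that DLT items are recorded in the expansion phase.
4. Reconcile the end of 4.1.2 (expansion once level 0 shows no DLTs) with 9.1.1 (at most 1 of 6).

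A formal acceptance limit on the bound is optional and for the sponsor to choose. If one is set, the allowable count depends on the evaluable number. With an illustrative limit of 1/3, 3/24 would meet it (29.2%) and 3/20 would not (34.4%).

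**Cost.** No extra patients. The work is in data capture: grade 4 events during treatment attributed to RT, and the opioid and diet items for persistent mucositis at 3 months, must be taken from the existing adverse event assessments and from standard-of-care visit records. Since weekly expansion visits are not trial procedures, the 1- and 3-month visits alone may miss events during treatment. The headline may also be less favourable than a bare statement that an MTD was found.

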RO-APM	Radiation Oncology-Alternative Payment Model
ROSAC	Radiation Oncology Safety Assurance Committee
RT	Radiation Therapy
SAE	Serious Adverse Event
SCCC	Simmons Comprehensive Cancer Center
SD	Stable Disease
UPIRSO	Unanticipated Problems Involving Risks to Subjects or Others
UTSW	University of Texas Southwestern Medical Center
UW-QOL	University of Washington Quality of Life Questionnaire
VMAT	Volumetric Modulated Arc Therapy

STUDY SCHEMA

STUDY SUMMARY

Title	HYHOPE: Phase I study of de-intensified hypofractionated radiation therapy for human papilloma virus-associated oropharynx cancer
Short Title	HYHOPE: De-intensified hypofractionated radiation therapy for HPV-associated oropharynx cancer
Protocol Number	STU 2020-1079
Phase	Phase I
Methodology	Rolling 6 dose finding cohort followed by dose expansion cohort
Study Duration	3 years to accrue, additional 1 year of follow-up
Study Center(s)	Single-center
Objectives	To assess the maximum tolerated dose/fractionation and signal for efficacy of de-intensified hypofractionated radiotherapy for favorable HPV-associated oropharynx cancer
Number of Subjects	24
Diagnosis and Main Inclusion Criteria	T1-3 (≤ 6 cm), N0-2 (except T1-2N0) p16 positive oropharyngeal squamous cell carcinoma with ≤ 10 pack-year smoking history
Study Product(s), Dose, Route, Regimen	Hypofractionated intensity modulated radiotherapy with concurrent chemotherapy (weekly cisplatin)
Duration of administration	3-4 weeks
Reference therapy	Conventionally fractionated radiotherapy (60-70 Gy) over 6-7 weeks with concurrent chemotherapy (historical control)
Statistical Methodology	Phase I: standard rolling 6 design to determine the maximum tolerated dose/fractionation. Additional patients will be enrolled to reach 24 patients to achieve 20 evaluable patients for the clinical response endpoint assuming a 15% attrition rate.

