9.1.3 Secondary endpoints

- Physician-reported acute and late toxicities
 - Rate of \geq grade 3 acute toxicities during treatment, and at 1 and 3 months after treatment using CTCAE v5.0
 - Rate of \geq grade 3 late toxicities at 6 and 12 months after treatment using CTCAE v5.0
- Oncologic outcomes: LRC, PFS, and OS from start of treatment
- Patient-reported QOL:

- MDADI, UW-QOL, and EQ-5D-5L scores at baseline, 1, 3, 6, and 12 months after treatment
- Feeding tube dependence rate at baseline, 1, 3, 6, and 12 months after treatment

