9.2 Sample Size and Accrual

We anticipate 3-6 patients in each cohort with a maximum of 12 total patients (e.g. 6 in level 0, 6 in level 1 or -1) during the Rolling 6 dose escalation phase.

During the dose expansion phase, patients will be accrued until a total sample size of 24 is reached to ensure at least 20 evaluable patients at 1 year assuming an attrition rate of 15%. We anticipate accruing 3 patients per month for a total accrual period of approximately 3 years accounting for time to reach the primary endpoint at 3 months prior to enrolling on to the next cohort.

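### Section 7.5 uses a single locoregional-recurrence boundary, set at the hypothesised 85% with no allowance for sampling error, both to pass the hypothesis and to stop for futility; the accrual figures also conflict

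*Combined protocol and SAP*

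**What the plan says.** **The LRC rule (section 7.5).** "The secondary hypothesis is that the crude 1-year LRC rate is at least 85% (based on historical controls"). For the target of 20 evaluable patients, up to three "patients can have a LRR and satisfy the pre-specified hypothesis". The trial is to be terminated for futility "if a 4th patient enrolled on the trial experiences LRR within 1 year of completing the study treatment".

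**Sample size (section 9.2).** Accrual runs to 24 patients, to give "at least 20 evaluable patients at 1 year assuming an attrition rate of 15" per cent.

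**Analysis.** Section 9.3.2.1 plans a cumulative-incidence estimate with death as a competing risk, and mentions no interval. Section 9.1.3 lists "Oncologic outcomes: LRC, PFS, and OS from start of treatment", whereas section 7.5 counts from completion of treatment. No section gives an unacceptable LRC rate, an error rate, a confidence bound or trigger probabilities for the rule.

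**Accrual.** Section 9.2: "We anticipate accruing 3 patients per month for a total accrual period of approximately 3 years", a figure it describes as allowing for the 3-month DLT waits. The study summary gives "3 years to accrue, additional 1 year of follow-up". Under section 9.1.1, once six patients are enrolled at a level, "enrollment will stop until at least 5 of the 6 patients have completed evaluation for DLT".

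**The concern.** The pass cut equals the expected number of recurrences at 85% control. A regimen that exactly meets the hypothesis would produce a fourth recurrence by ordinary chance in a sizeable share of trials. A regimen somewhat below 85% would often be reported as meeting it. This is the only numerical efficacy threshold in the document, it carries mandatory termination, and its properties are not shown to those who approve or monitor the trial.

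The accrual conflict bears on the same rule. How much follow-up exists when the last patient enrols determines whether the rule can limit enrolment or only label the trial afterwards.

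**Working it through.** **1. The plan's own figures reproduce.** 20 x (1 - 0.85) = 3 LRRs, so the pass cut is 17/20 = 85%. 20/0.85 = 23.5, rounded up to 24; 24 x 0.85 = 20.4 evaluable. The issue is where the cut sits, not a miscalculation. The trigger is the next outcome: 16/20 = 80%, or 20/24 = 83.3% if all enrolled patients are followed.

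**2. Probability of a fourth LRR.** With X the number of LRRs, binomial(n, p) and p = 1 - LRC, the trigger probability is P(X >= 4) = 1 - P(X <= 3). For n = 20 and p = 0.15: 1 - (0.0388 + 0.1368 + 0.2293 + 0.2428) = 1 - 0.6477 = 0.352. The attrition column uses n = 24 and p = 0.85 x (1 - LRC). It assumes that 15% are lost independently, before any LRR is seen.

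| True 1-year LRC | n = 20 | 24 enrolled, 15% lost | 24, none lost |
|---|---|---|---|
| 75% | 77.5% | 78.2% | 88.5% |
| 80% | 58.9% | 60.1% | 73.6% |
| 85% | 35.2% | 36.7% | 49.5% |
| 90% | 13.3% | 14.2% | 21.4% |
| 95% | 1.6% | 1.8% | 3.0% |

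The cut was derived for 20 evaluable patients, but the trigger counts any enrolled patient. The last column is therefore a possible case.

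**3. Probability of passing when LRC is below 85%.** At a true 80%, P(X <= 3) is 41.1% for n = 20 and 26.4% for n = 24. At 75% it is 22.5% and 11.5%.

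**4. What 17/20 shows.** Exact (Clopper-Pearson) two-sided 95% limits are 62.1-96.8% for 17/20, 75.1-99.9% for 19/20 and 83.2-100% for 20/20. One-sided 95% lower limits are 65.6% for 17/20, 78.4% for 19/20 and 86.1% for 20/20 (0.05^(1/20)). Only 20/20 clears 85%, and only one-sided.

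**5. Clocks.** Section 5.3 places the last visit 12 months after completion. Per-protocol RT at the remaining levels takes 18-28 elapsed days (section 4.1.4.3), so that visit falls nominally 12.6-12.9 months after start. An LRR first found there counts under section 7.5 but falls outside a 1-year estimate from start.

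**6. Accrual.** 24/3 = 8 months of enrolling, plus holds. With one level, first patient at time 0: the fifth patient enters at 1.33 months, and 1.33 + 0.62 (19 days of RT) + 3 = 4.95 months, when the hold lifts. The other 18 patients then enter at 3 per month, the last at 4.95 + 17/3 = 10.6 months. Starting one interval later, and resuming one interval after the hold lifts, gives 11.3. Two levels (0, then -1 with 26 days of RT) give 13.8-14.8 under the same two conventions. Solving for 36 months gives about 0.65-0.77 patients per month.

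| At last enrolment | Past 3-month visit | Past 1 year after RT |
|---|---|---|
| 3 per month, one level | 13 of 24 | 0 |
| 3 per month, two levels | 12 of 24 | 4-6 |
| 36-month accrual | 21 of 24 | 14-15 |

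These counts assume even arrivals, full-length holds, no lag from enrolment to RT and no replacements.

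**The case against.** **The floor is the worst admissible case.** This stands. Section 1.1 cites 2-year PFS of 86% and 90.5% with 60 Gy regimens. If PFS there counts LRR, distant metastasis and death, as section 6.1.1 does, 1-year LRC in those series was at least that high. If the new regimen performs similarly, the trigger probability lies below the 85% row and may be near or under the 90% row. Section 5.3 also excludes residual nodal disease at neck dissection from failure, which lowers the count. But the hypothesis includes 85%, and the plan shows none of these probabilities.

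**No formal test is promised.** This also stands. The rate is crude, the endpoint secondary, the trial phase I, and section 9.3.2.1 plans estimation. A reader might infer a failed hypothesis test; the documents set none up. The objection leaves untouched the wording that a count satisfies a pre-specified hypothesis.

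**A strict limit can be defended when a curative treatment is de-intensified.** True, and the limit may stay. A reader might infer that it was meant to be conservative, but no section says so.

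**The clock difference is small.** Agreed: 18-28 days is no wider than the visit window of 4 weeks either way, and section 9.3.2.1 names no 1-year landmark. One origin should still be stated.

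**The accrual arithmetic depends on conventions.** It does, by about a month either way. No convention tried comes near 36 months.

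**Conclusion.** The point holds. Section 7.5 places one boundary at the hypothesised rate: observed LRC of 85% or more in 20 patients passes, and the next outcome ends the trial. At a true 85% the trigger is met 35-50% of the time, depending on how many of the 24 enrolled are followed and whether lost patients' recurrences are seen. A result of 17/20 does not establish at least 85%. These figures assume independent patients with a common LRR probability.

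Stronger readings are not supported. The trigger is not itself at 17/20. Meeting it is not the same as stopping early, because recurrences may be found after enrolment ends. Nor does the absence of 1-year follow-up at 3 per month mean that the rule cannot act: recurrences found earlier count, and 12-13 patients would be past the 3-month visit at last enrolment. The MTD determination is unaffected.

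The accrual statements cannot both be right: 3 per month implies roughly 11-15 months. This is a separate correction, with high confidence in its direction. The whole is worth fixing, but it concerns a secondary endpoint.

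**What to change.** **Section 7.5.** Replace the statement that up to three LRRs satisfy the hypothesis with a commitment to report the observed 1-year LRC, its denominator and its exact 95% confidence interval. State the four-LRR trigger probabilities for 20 to 24 patients: about 78-89%, 59-74%, 35-50%, 13-21% and 2-3% at true LRC of 75, 80, 85, 90 and 95%. Leave the limit and its consequence to the sponsor, and attribute no intent to it.

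**Sections 9.3.2.1, 9.1.3 and 7.5.** Report the 1-year cumulative incidence of LRR with a 95% confidence interval. Use one time origin throughout, and say whether an LRR found at the 12-month visit, with its window, counts.

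**Section 9.2 and study summary.** State the true accrual rate and a duration that follows from it. Say whether the futility rule can be expected to act before enrolment ends.

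**Cost.** Wording only, with no added patients or visits. The downside is that the efficacy statement becomes descriptive, with a wide interval.
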